APPENDIX G –ASSESSMENT OF PRIOR AND CUMULATIVE ANTHRACYCLINE/ANTHRACENEDIONE EXPOSURE*

	Cumulative Dose Conversion		Daunorubicin isotoxic Dose Equivalent
Doxorubicin:	mg/m ²	Cumulative dose x 1.00 =	mg/m ²
Daunorubicin:	mg/m ²	Cumulative dose x 1.00 =	mg/m ²
Mitoxantrone:	mg/m ²	Cumulative dose x 4.00 =	mg/m ²
Idarubicin:	mg/m ²	Cumulative dose x 5.00 =	mg/m ²
Epirubicin:	mg/m ²	Cumulative dose x 0.67 =	mg/m ²
Patients who have received more than one anthracycline should have each individual agent cumulative dose converted to daunorubicin dose equivalents using these conversion factors, and then added together.			Total Daunorubicin Dose Equivalent: mg/m ²

* adapted from Long-Term Survivor Guidelines, Version 4.0. October, 2013 ©Children's Oncology Group

List of Appendices

Appendix 1. Criteria for Grading Severity of Clinical Tumor Lysis Syndrome.....	33
Appendix 2. Sample Summary Table Templates	34

1. Synopsis

Protocol Title:

A Phase 2, Randomized, Biomarker-Driven, Clinical Study in Patients with Relapsed or Refractory Acute Myeloid Leukemia (AML) with an Exploratory Arm in Patients with Newly Diagnosed High-Risk AML and Exploratory Arms with Varying Levels of MCL-1 Dependence

Study Design:

There is a primary study component and four exploratory study arms

- Primary Study: single-arm, Simon two-stage lead in to confirm efficacy assumptions followed by a randomized, two-arm parallel design
- Exploratory Study Arms: single-arm observational

Study Populations:

- Primary Study: Relapsed and refractory AML patients with MCL-1 dependence $\geq 40\%$
- Exploratory Study Arms:
 - Patients with newly diagnosed, high-risk AML and MCL-1 dependence $\geq 40\%$
 - Relapsed and refractory AML patients with MCL-1 dependence between 0% and $< 15\%$
 - Relapsed and refractory AML patients with MCL-1 dependence between 15% and $< 30\%$
 - Relapsed and refractory AML patients with MCL-1 dependence between 30% and $< 40\%$

Treatment Arms:

- ACM (alvocidib, Ara-C [cytarabine] and mitoxantrone)
- CM (Ara-C [cytarabine] and mitoxantrone)

Biomarker:

- MCL-1 dependence measured by mitochondrial sensitivity to NOXA BH3 peptides (hereafter referred to as MCL-1 dependence)

Sample Size:

- Primary Study, Stage 1: up to 23 patients
- Primary Study, Stage 2: 106 patients (53 patients per treatment arm)
- Exploratory Study Arms: 20 patients in each of four exploratory patient populations

Randomization:

- Primary Study, Stage 1: Not randomized, all patients receive ACM

- Primary Study, Stage 2: Randomized 1:1 to ACM or CM stratified by response to frontline AML therapy
- Exploratory Study Arms: Not randomized, all patients receive ACM

Analysis Populations:

Intent-to-treat (primary for efficacy), safety, response-available, per-protocol, crossover

Response Assessments:

Central review performed by a panel of independent, expert hematologists according to an approved charter under change control (primary response assessment); local review of bone marrow and blood test results by the investigator at the study center where patient is enrolled (secondary assessment); “sponsor review” by employees and/or agents of Tolero Pharmaceuticals

Missing Values:

Missing values will not be replaced by imputed values. Patients who do not supply bone marrow for response assessment are counted among those not achieving remission. Missing time-to-event endpoints will be censored using standard rules detailed below.

Interim Analysis:

Single interim analysis after cycle-1 responder status is established for 28 patients per treatment arm; O’Brien-Fleming boundaries to control type-1 error rate

Significance Level:

One-sided, 2.5% including control for interim analysis and multiple comparisons

Procedure for Multiple Comparisons:

Hierarchical closed test procedure

Efficacy Endpoints:

Cycle-1 CR rate (primary endpoint), cycle-1 combined CR rate, cycle-1 combined remission rate, stem cell transplant rate, overall survival, progression-free survival, relapse-free survival, CR duration

Safety Endpoints:

30- and 60-day survival, adverse events, time to neutrophil recovery, time to platelet recovery, prevalence of tumor lysis syndrome, clinical laboratory parameters, vital signs

Statistical Methods:

Treatment-arm comparisons of cycle-1 complete remission rates (primary efficacy endpoint) and stem cell transplant rates by stratified CMH general association test (primary analysis) and logistic regression (supportive analyses); comparisons of time-to-event endpoints (progression-free survival, overall survival, relapse-free survival, and complete remission duration) by stratified log rank test (primary analysis) and Cox PH models (supportive analyses)

2. Abbreviations

Standard abbreviations (e.g., AML = acute myeloid leukemia and mg = milligrams) are omitted intentionally.

ACM	Alvocidib, Ara-C (Cytarabine) and Mitoxantrone
AE	Adverse Event
ANC	Absolute Neutrophil Count
ATC	Anatomical and Therapeutic Class
AUC	Area Under Curve
BM	Bone Marrow
BSA	Body Surface Area
CI	Confidence Interval
CM	Ara-C (Cytarabine) and Mitoxantrone
CMH	Cochran-Mantel-Haenszel (test)
CR	Complete Remission
CRi	Complete Remission with Incomplete Blood Count Recovery
CRp*	Complete Remission with Incomplete Platelet Recovery
CTCAE	Common Terminology Criteria for Adverse Events
DDE	Drug Dictionary Enhanced
DSMB	(Independent) Data Safety Monitoring Board
ECOG	Eastern Cooperative Oncology Group (performance status)
HR	Hazards Ratio
ITT	Intent-to-Treat (patient population)
IWG	International Working Group
KM	Kaplan-Meier (survivor function estimate)
LR	Logistic Regression
MedDRA	Medical Dictionary for Regulatory Activities
OS	Overall Survival
PBSC	Peripheral Blood Stem Cells
PFS	Progression-Free Survival
PH	Proportional Hazards (model)

* The term CRp appears in this document to maintain compatibility with the study's case report forms, however CRp will not be used by the hematologists performing the central review of patients' responses and it is not expected to be used by the investigators.

PR	Partial Remission
PT	(MedDRA) Preferred Term
RFS	Relapse-Free Survival
ROC	Receiver Operating Characteristic (curve)
SAE	Serious Adverse Event
SAP	Statistical Analysis Plan
SCT	Stem Cell Transplant/Transplantation
SMQ	Standardized MedDRA Query
SOC	(MedDRA) System Organ Class
TEAE	Treatment Emergent Adverse Event
TLS	Tumor Lysis Syndrome
WHO	World Health Organization

3. Definitions

Standard statistical terminology (e.g., type-1 error rate and significance level) is omitted intentionally. Efficacy endpoints are defined in Section 4.1 below (see Table 1).

Baseline Value: last measured value prior to the first dose of study drug (or prior to randomization for patients not treated)

Combined CR: response assessment of CR, CRi or CRp

Combined Remission: response assessment of CR, CRi, CRp or PR

Crossover Patient: a patient randomized to CM who, following 1-2 cycles of CM, receives ACM as stipulated in the study protocol

Cycle 1: period of time from the first dose of study drug until the start of study drug in cycle 2 or the start of alternative AML therapy other than supportive measures such as blood product transfusions (hence a patient whose first response assessment in cycle 1 is a CRi or CRp is considered to have achieved CR if neutrophils and platelets recover prior to initiation of cycle 2 or alternative AML therapy)

Cycle-1 Combined CR Rate: percentage of patients who achieve a combined CR (CR, CRi or CRp) after one cycle of treatment

Cycle-1 Combined Remission Rate: percentage of patients who achieve a combined remission (CR, CRi, CRp or PR) after one cycle of treatment

Cycle-1 CR Rate: percentage of patients who achieve a CR after one cycle of treatment (see section 7.9.1)

Intent-to-Treat Population: all patients randomized to receive study drug regardless of whether they actually received study drug and regardless of whether evidence is found indicating they failed to meet study inclusion/exclusion criteria or had other protocol violations (see section 7.1)

Neutrophil Recovery: Absolute neutrophil count $\geq 1 \times 10^9/L$ following the administration of study drug

Per-Protocol Population: The subset of safety patients who either (a) have at least one response assessment on study, or (b) die prior to their first scheduled response assessment; however, patients are excluded from the per-protocol population if they have an important protocol deviation, such as when evidence is found indicating they failed to meet any study inclusion/exclusion criterion (see section 7.1)

Platelet Recovery: Platelet count $\geq 100 \times 10^9/L$ following the administration of study drug

Pointwise: without controlling for multiple comparisons

Prestudy: Occurrence prior to randomization

Response-Available Population: The subset of safety patients who have at least one response assessment on study (see section 7.1)

Safety Population: The subset of intent-to-treat patients who received at least one dose of study drug (see section 7.1)

Sensitivity Analysis: study of how statistical methodology and assumptions affect results of the primary analysis

Shift Table: two-way frequency table pairing baseline value with the most extreme post-baseline result

Study Drug: alvocidib, Ara-C (cytarabine) and mitoxantrone

Supportive Analysis: synonymous with Sensitivity Analysis

Treatment Failure: failing to achieve a CR, CRi, CRp or PR following induction therapy (see section 7.9.2)

4. Introduction

This Statistical Analysis Plan (SAP) details the planned methodology for summarizing data collected in the clinical study conducted under Tolero, Inc. protocol TPI-ALV-201 and for comparing outcomes between the two treatment arms, ACM (alvocidib, Ara-C [cytarabine] and mitoxantrone) and CM (Ara-C [cytarabine] and mitoxantrone). The current version of the study protocol is Amendment 7 dated 30-MAY-2018. Future protocol amendments (if any) will be reviewed to assess whether the changes necessitate modification of this SAP.

Since the study protocol is a companion document to this SAP, aspects in the protocol unrelated to statistical issues (e.g., patient eligibility criteria, descriptions of clinical materials, and criteria for defining treatment failure, response to treatment and disease relapse) are not repeated here.

4.1. Study Endpoints

Statistical analysis and/or summarization is planned for the following study endpoints. Complete details on how endpoints are calculated and compared across treatment arms are presented in the subsections below. A key to abbreviated terms appears in Section 2.

Table 1. Study Endpoints

Primary Efficacy Endpoint
 
• Cycle-1 CR Rate: percentage of patients who achieve a CR after one cycle of treatment

Secondary Efficacy Endpoints (not listed in order of importance)
 
• Cycle-1 Combined CR Rate: percentage of patients achieving a combined CR (CR, CRi or CRp) after one cycle of treatment• Cycle-1 Combined Remission Rate: percentage of patients achieving a combined remission (CR, CRi, CRp or PR) after one cycle of treatment• Overall Survival: time from the date of randomization (Day 1) until death from any cause• Progression-Free Survival: time from the date of randomization (Day 1) until (a) treatment failure, (b) relapse after combined remission (CR, CRi, CRp or PR), or (c) death from any cause, whichever occurs first• Relapse-Free Survival Following CR (defined only for patients who achieve a CR during the study): time from the date of CR (Day 1) until (a) relapse after CR, or (b) death from any cause, whichever occurs first• Relapse-Free Survival Following Combined CR (defined only for patients who achieve a combined CR during the study): time from the earliest date of combined CR (Day 1) until (a) relapse after combined CR, or (b) death from any cause, whichever occurs first• Relapse-Free Survival Following Combined Remission (defined only for patients who achieve a combined remission during the study): time from the earliest date of combined remission (Day 1) until (a) relapse after combined remission, or (b) death from any cause, whichever occurs first• CR Duration (defined only for patients who achieve a CR during the study): time from the date of CR (Day 1) until relapse after CR• Combined CR Duration (defined only for patients who achieve a combined CR during the study): time from the earliest date of combined CR (Day 1) until relapse after combined CR• Combined Remission Duration (defined only for patients who achieve a combined remission during the study): time from the earliest date of combined remission (Day 1) until relapse after combined remission• Stem Cell Transplant Rate: percentage of patients proceeding directly to stem cell transplantation within 90 days after their last dose of study drug

Table 1. Study Endpoints

Safety Endpoints (not listed in order of importance) 
• 30- and 60-Day Mortality• Adverse Event Incidence Rates• Time to neutrophil recovery $\geq 1 \times 10^9/L$• Time to platelet recovery $\geq 100 \times 10^9/L$• Presence and Severity of Tumor Lysis Syndrome• Clinical Laboratory Parameters• Vital Signs
Other Endpoints 
• Concomitant Medication Usage Rates

4.2. Statistical Objectives

The statistical objectives are fourfold:

1. To establish the statistical significance at a controlled, one-sided 2.5% significance level, the superiority of the ACM cycle-1 CR rate in relapsed/refractory AML patients with baseline MCL-1 dependence $\geq 40\%$ compared to that for CM treatment
2. To demonstrate the statistical significance of the superiority of ACM treatment compared to CM with respect to secondary measures of efficacy while controlling for the inflationary effects of multiple comparisons on the overall significance level
3. To model the relationship between baseline MCL-1 dependence and response to treatment with ACM
4. To describe the safety of ACM treatment in relapsed/refractory and newly diagnosed, high-risk AML patients (safety in relapsed/refractory AML patients will be judged relative treatment with CM)

5. Sample Size

5.1. Primary Study

5.1.1. Stage 1

The sample size of 23 eligible patients for stage 1 was selected because it allows estimation of the CR rate by means of a 90% confidence interval with maximum width of $\pm 17\%$. Although this study does not follow a Simon 2-stage design, 23 patients is consistent with the sample size for stage 1 of the Simon 2-stage minimax design with 80% power for testing the null hypothesis that the CR rate is 50% against a one-sided alternative at the 5% level of significance when the actual CR rate is 70%. In the Simon

2-stage design described, the study would continue to stage 2 only if 13 patients achieve remission out of a maximum of 23 eligible patients. Therefore, this was selected as the requirement to proceed to stage 2 of this study.

5.1.2. Stage 2

The total planned sample size of 106 patients (53 per treatment arm) in stage 2 of the primary study provides 90% power to reject the null hypothesis of equal cycle-1 CR rates across treatment arms under the following conditions:

- Cycle-1 CR rates of 70% and 40% for patients receiving ACM and CM, respectively
- One-sided 2.5% significance level
- A single interim analysis of cycle-1 CR rates using O’Brien-Fleming boundaries¹ (see section 7.5.1) after responder status has been defined for 56 patients (28 per treatment arm)
- Randomization based on a 1:1 patient allocation ratio (ACM to CM)

Table 2 lists the programming statements used in SAS (version 9.4) to compute the sample size. Relevant SAS output is shown in Table 3 and Table 4.

Table 2. SAS Programming Statements for Sample Size Calculation

```
proc seqdesign boundaryscale=pvalue;
    design alpha=0.025 alt=upper beta=0.1 info=cum(56 106) method=obf nstages=2;
    samplesize model=twosamplefreq(nullprop=0.40 prop=0.70 test=prop weight=1);
run;
```

Table 3. SAS PROC SEQDESIGN Output: Boundary Information

Stage				Alternative	Boundary Values
	Information Level			Reference	Upper
	Proportion	Actual	N	Upper	Alpha
1	0.5283	62.2073	55.98657	2.36615	0.00321
2	1.0000	117.7495	105.9746	3.25537	0.02378

Table 4. SAS PROC SEQDESIGN Output: Sample Sizes

Stage	Fractional N				Ceiling N			
	N	N(Grp 1)	N(Grp 2)	Information	N	N(Grp 1)	N(Grp 2)	Information
1	55.99	27.99	27.99	62.2073	56	28	28	62.2222

Table 4. SAS PROC SEQDESIGN Output: Sample Sizes

Stage	Fractional N				Ceiling N			
	N	N(Grp 1)	N(Grp 2)	Information	N	N(Grp 1)	N(Grp 2)	Information
2	105.97	52.99	52.99	117.7	106	53	53	117.8

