	
point after confirming CR, CRi or CRp responses in 13 Stage-1 patients.
 
The sample size of 23 eligible patients for Stage 1 was selected because it allows estimation of the remission rate by means of a 90% confidence interval with maximum width of $\pm 17\%$. Although this study does not follow a Simon 2-stage design, 23 patients is consistent with the sample size for Stage 1 of the Simon 2-stage minimax design with 80% power for testing the null hypothesis that the remission rate is 50% against a one-sided alternative at the 5% level of significance when the actual remission rate is 70%.
 
In the Simon 2-stage design described, the study would continue to Stage 2 only if 13 patients achieve remission out of 23 eligible patients. Therefore, this was selected as the requirement to proceed to Stage 2 of this study. However, the study may proceed to Stage 2 as soon as 13 patients achieve remission.
 
In Stage 2, patients will be randomized to receive either ACM or CM.
 
The planned sample size of 56 patients (28 per treatment arm) in Stage 2 of this study provides 90% power to reject the null hypothesis of equal CR rates across treatment arms under the following conditions:
 
• CR rates of 70% and 30% for patients receiving ACM and CM, respectively• One-sided 2.5% significance level• Randomization based on a 1:1 patient allocation ratio (ACM to CM)• No interim analysis 
Randomization to treatment arm will be stratified by:
 
• Response to first-line therapy:
○ Refractory: persistent disease or complete remission [CR] duration <90 days○ Early relapse: CR duration 90 days to 1 year○ Late relapse: CR duration >1 year but <24 months 
Response assessments in Stage 1 are defined by the International Working Group Criteria and 2010 European LeukemiaNet (ELN). The 2017 ELN criteria will be used to determine patient responses during Stage 2. Response assessments will include:
 
• CR rate = Percentage of patients achieving CR• Combined CR rate (CR+CRp[†]+CRi)• Combined Response Rate (CR+CRp[†]+CRi+PR)• Overall Survival (OS)• Event-free Survival (EFS)• Rate of Stem Cell Transplantation
--	---

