11.2 Sample Size

11.2.1 Sample Size in Stage 1

The sample size of 23 eligible patients for Stage 1 was selected because it allows estimation of the remission rate by means of a 90% confidence interval with maximum width of ±17%. Although this study does not follow a Simon 2-stage design, 23 patients is consistent with the sample size for Stage 1 of the Simon 2-stage minimax design with 80% power for testing the null hypothesis that the remission rate is 50% against a one-sided alternative at the 5% level of significance when the actual remission rate is 70%. In the Simon 2-stage design described, the study would continue to Stage 2 only if 13 patients achieve remission out of a maximum of 23 eligible patients. Therefore, this was selected as the requirement to proceed to Stage 2 of this study. However, the study may proceed to Stage 2 as soon as 13 patients achieve remission.

The primary objective of Stage 1 is to determine the CR rate in patients with relapsed or refractory AML with MCL-1 dependence of $\geq 30\%$. Thus a patient who leaves the study prior to providing a bone marrow sample adequate for assessing response to treatment will be replaced by another eligible patient.

11.2.2 Sample Size in Stage 2

The planned sample size of 56 patients (28 per treatment arm) in Stage 2 of this study provides 90% power to reject the null hypothesis of equal CR rates across treatment arms under the following conditions:

- CR rates of 70% and 30% for patients receiving ACM and CM, respectively
- One-sided 2.5% significance level
- Randomization based on a 1:1 patient allocation ratio (ACM to CM)

The primary objective of Stage 2 is to compare CR rates between patients with relapsed or refractory AML with MCL-1 dependence of $\geq 30\%$ receiving 1 cycle of ACM treatment and those receiving 1 cycle of CM. Thus a patient who leaves the study prior to receiving one course of study treatment will be replaced by another eligible patient.

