7.4. Interim Analysis

A single interim analysis is planned when cycle-1 response has been defined for 28 patients per treatment arm. Cycle-1 response may be available for more than 28 patients in one treatment arm when the alternate treatment arm reaches 28 because the enrollment ratio may not be precisely 1:1 over time. The additional patients in the faster-enrolling treatment arm will be included in the interim analysis. Therefore, the interim analysis sample size may be slightly more than 56 patients.

Cycle-1 CR rate (the primary efficacy endpoint) will be tested using the statistical procedures described below. As shown in Table 3, a p-value ≤ 0.00321 is required to reject the null hypothesis of equal cycle-1 CR rates across treatment arms.

Measures taken to counter the effect of the interim analysis and maintain an overall 2.5% significance level are presented in section 7.5.1.

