7.4.1. Outcomes and Study Continuation

Two outcomes are possible from the interim analysis: statistical significance or nonsignificance. In the event of a nonsignificant difference between ACM and CM Cycle-1 CR rates (p-value > 0.00321), the study will continue to accrue and randomize patients.

If the interim analysis result for the primary analysis of Cycle-1 CR rate (see section 7.9.1) is statistically significant (p-value ≤ 0.00321), then randomization will be stopped. Additional eligible stage-2 patients will be enrolled into the study to receive open-label ACM until the planned enrollment of 53 ACM patients is complete. No additional patients will be enrolled into the CM treatment arm. Terminating randomization after the interim analysis will have a negative effect on the power to declare treatment differences in secondary endpoints as statistically significant, however it is understood from polling investigators that they would be unwilling to enroll patients into the study once ACM has been established as superior to CM with respect to Cycle-1 CR rate.

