7.5.2. Type-1 Error Rate Control for Multiple Comparisons

Without taking appropriate measures, testing multiple efficacy parameters inflates the overall significance level since the probability of making a type-1 error in at least one from a set of hypothesis tests is greater than the probability of making a type-1 error in any single test. The hierarchical closed test procedure^{3,4} will be used to maintain the overall 2.5% significance level.

The order of efficacy endpoints for the hierarchical closed test procedure is:

1. Cycle-1 CR rate
2. Progression-Free Survival
3. Stem Cell Transplant Rate
4. Cycle-1 Combined CR Rate
5. Cycle-1 Combined Remission Rate
6. Overall Survival
7. Combined Remission Duration
8. Combined CR Duration
9. CR Duration

The final analysis will be conducted at a one-sided 2.378% significance level using the statistical procedures described below. Cycle-1 CR rate, the primary efficacy endpoint, will be declared statistically significant if its test p-value ≤ 0.02378 . A secondary efficacy endpoint will be declared statistically significant only if its test p-value ≤ 0.02378 and all efficacy endpoints preceding it in the hierarchy are statistically significant. In other words, declaration of statistical significance for efficacy endpoints will advance in order down the hierarchy only until a p-value > 0.02378 is found.

In addition, although primary and supportive analytical methods are specified for each endpoint in the hierarchy, only the p-value from the primary analysis will be used for deciding statistical significance. Supportive (sensitivity) analyses are to demonstrate the robustness of primary results to slight modifications to how endpoints are defined and/or analyzed.

Declarations of statistical significance will not be advanced for endpoints not included in the hierarchy of the closed test procedure (e.g., ECOG performance status).

It is worthwhile noting...

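### The SAP supplied was written for Amendment 7, and its Stage 2 size, interim look, significance threshold and secondary test order contradict the current protocol

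*SAP*

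**What the plan says.** SAP section 4 names Amendment 7 (30 May 2018) as the current protocol and undertakes to review later amendments for their effect on the SAP. Protocol section 2.7 describes the main change made by Amendment 11. For Stage 2 the two documents then read as follows.

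| Item | Protocol | SAP |
|---|---|---|
| Size | "The planned sample size of 56 patients (28 per treatment arm) in Stage 2 of this study provides 90% power" (11.2.2) | "The total planned sample size of 106 patients (53 per treatment arm) in stage 2 of the primary study provides 90% power" (5.1.2) |
| CR rates assumed, ACM vs CM | 70% vs 30% | 70% vs 40% |
| Interim | "No interim analysis" (Study Summary) | "A single interim analysis is planned when cycle-1 response has been defined for 28 patients per treatment arm" (7.4) |
| Threshold | one-sided 0.025 for every endpoint (11.4.2) | 0.00321 at the interim (7.4); "The final analysis will be conducted at a one-sided 2.378% significance level" (7.5.2) |
| Test order | CR, combined CR, combined response, OS, EFS, transplant rate | CR, PFS, transplant rate, combined CR, combined remission, OS, three duration endpoints |
| Relapse event | EFS: relapse after CR, censored at 2 years | PFS: relapse after CR, CRi, CRp or PR, no 2-year censoring |
| MCL-1 cutoff | ≥30%, but the Stage 2 text under Study Treatment in the Study Summary still says ≥40% | ≥40% |
| Stage 2 AE grading | CTCAE v5.0 | CTCAE v4.03 |

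SAP 7.4.1 gives two outcomes at the interim. If it is not significant, "the study will continue to accrue and randomize patients". If it is significant, randomisation stops, but "Additional eligible stage-2 patients will be enrolled into the study to receive open-label ACM until the planned enrollment of 53 ACM patients is complete".

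Protocol section 11 says a full SAP will be finalised before database lock.

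**The concern.** Both documents are live text, and they cannot both be followed. At 28 patients per arm the protocol ends Stage 2 and tests at 0.025. At the same point the SAP takes an interim look at 0.00321 and ends enrolment on neither branch.

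The hierarchies also permit different claims. Suppose CR and combined CR pass and PFS fails. Combined CR can be claimed under the protocol, where it is tested second. It cannot under the SAP, where "2. Progression-Free Survival" comes ahead of it and blocks everything below.

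Treatment is open-label. If the conflict stays open until database lock, the choice between the two rules could be made with knowledge of the results.

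**Working it through.** **1. Reproduce the SAP's 106.** Inputs from SAP 5.1.2: 70% vs 40%, one-sided α = 0.025, power 90%, information fraction t = 56/106 = 0.5283, O'Brien-Fleming.
- Solve P(Z₁ ≥ c/√t or Z₂ ≥ c) = 0.025 under the null, with correlation √t. This gives c = 1.9813.
- Boundary p-values: 1 − Φ(c/√t) = 0.00321 and 1 − Φ(c) = 0.02378, as stated.
- Drift for 90% power = 3.2554. Information = (3.2554/0.30)² = 117.75.
- Patients per arm = 117.75 × (0.7×0.3 + 0.4×0.6) = 117.75 × 0.45 = 52.99. Total 105.97, so 106.

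**2. Reproduce the protocol's 56.** Inputs from Protocol 11.2.2: 70% vs 30%, one-sided 0.025, power 90%, no interim.
- n per arm = (1.960 + 1.282)² × (0.21 + 0.21)/0.40² = 27.6, so 28.
- Power at 28 = Φ(0.40/√(0.42/28) − 1.960) = Φ(1.306) = 90.4%.
- This uses the unpooled variance. The pooled formula would give 31 per arm, or 87.0% power at 28.

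Neither figure is an arithmetic error.

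**3. Size of the conflict at 28 per arm.** Every pair of binomial outcomes was enumerated with the single-stratum CMH statistic, z = (x₁ − x₂)/28 ÷ √(p̄(1 − p̄)·2/28) × √(55/56). Trials not significant at 0.00321 were then extended by 25 per arm and tested at 0.02378.

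| True rates | Pass 0.025 | Pass 0.00321 | Split | Split trials that win at 106 | Win under protocol, never under SAP |
|---|---|---|---|---|---|
| 70/30 | 85.9% | 59.3% | 26.7% | 99.4% | 0.16% |
| 70/40 | 60.7% | 29.2% | 31.6% | 95.7% | 1.3% |

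Split means success under the protocol but continued randomisation under the SAP.

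**4. One outcome.** With 18/28 vs 9/28, p̄ = 27/56 = 0.482, z = 0.3214/0.1335 × 0.991 = 2.385 and one-sided p = 0.0085. The protocol declares success and stops at 56. The SAP randomises up to 106 − 56 = 50 more patients.

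**5. Sensitivity.** The planned test is stratified and the stratum sizes are not given. Three strata were therefore simulated with assumed shares from equal thirds to 60/30/10, and with equal or unequal CR rates. The split was 23–26% at 70/30 and 31–32% at 70/40. By normal approximation at 70/30 it is 90.4% − 70.5% ≈ 20% (unpooled) or 87.0% − 61.5% ≈ 25% (pooled).

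**6. The 0.02378 level.** In the unstratified test at 28 per arm, no outcome with appreciable probability falls between 0.02378 and 0.025. In stratified simulations fewer than 1% of trials did. For CR this gap alone is immaterial.

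The level is, however, specific to a look at 56 of 106. The corresponding O'Brien-Fleming pairs are 0.00258 and 0.0240 for a look at 28 of 56, and 0.0100 and 0.0219 for a look at 42 of 56. Keeping the SAP interim at 56 and then testing 106 patients at 0.025 would give an overall one-sided α of 2.62%.

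**The case against.** The SAP is open about its basis, promises to review later amendments, and is due in final form only before database lock. A matching SAP may exist that was not supplied. That limits the finding to the SAP in hand but does not remove it: the protocol defers its analysis details to the SAP, and the only one available describes a different trial.

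The later protocol already fixes the size, threshold, primary test, ITT population and test order, so the room for a data-driven choice is smaller than it first looks. CR is also judged primarily by an independent panel (SAP 7.9.1). Both points have weight. But the documents do not call that panel blinded, and the SAP still presents a second, complete set of rules.

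On a significant interim, the SAP also stops randomisation at about 56 and declares superiority on CR then; only ACM enrolment goes on. That is correct, and it confines the disagreement over the randomised comparison to the split trials. The effect on whether CR eventually wins is small, as step 3 shows.

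**Conclusion.** The concern holds and must be fixed. Following the supplied SAP would apply a stopping point, threshold and hierarchy that the protocol no longer has. At 28 per arm the two documents would act differently in roughly 20–27% of trials if the rates are 70% and 30%, and in about 32% if they are 70% and 40%, with up to 50 more patients randomised. The loss of a CR win is rare (0.16% and 1.3% of all trials). The main consequences are when Stage 2 ends and which secondary results may be claimed.

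The headline percentages are from an unstratified test; the stratified figures rest on assumed stratum shares. That the supplied protocol is Amendment 11 is read from its section 2.7. The conclusion applies to the SAP supplied.

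**What to change.** Issue a SAP tied to the current amendment before any comparative look at Stage 2, and not merely before database lock.

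- **Design:** 56 patients, 70% vs 30%, no efficacy interim, 0.025 throughout. Remove sections 7.4 and 7.5.1 and the group-sequential design in Tables 2–4.
- **Hierarchy:** one order and one event-free endpoint, identical in both documents. As the protocol stands, that means its order and its EFS, including the 2-year censoring. If the sponsor prefers the SAP's, the protocol must be amended.
- **Interim:** state whether any efficacy look has taken place. If one has, recompute the final level from its actual timing and the actual final size, and do not carry over 0.02378.
- **MCL-1 cutoff:** reconcile the SAP, the body of the protocol and the Study Treatment text of the Study Summary.
- **AE grading:** align the Stage 2 CTCAE version.
- **Other conflicts to close in the same revision:** Stage 1 data are pooled with Stage 2 ACM data for secondary efficacy in Protocol 11.4 but barred from inference in SAP 7. Crossover patients count as ACM in the safety population in Protocol 11.3 but are excepted in SAP 7.1.

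The cost is a SAP revision and a one-line correction in the Study Summary. No patients or procedures are added. If a matching SAP already exists, producing it resolves the SAP side of the point.
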